## **VII. Criteria for Diagnosing and Grading Endpoints of Interest**

- 1) Acute toxicities induced by infusions of EBV-specific T-cells will be graded according to the NCI criteria used to grade organ toxicities induced by chemotherapeutic agents (48).
- 2) Allograft rejection episodes developing in organ transplant recipients will be diagnosed, assessed, and managed by the patient's transplant physician, utilizing standard criteria established for the identification and grading of rejection episodes in transplanted kidney, liver, heart or lung allografts (49-51).
- 3) Acute Graft vs. Host Disease will be diagnosed and graded utilizing the IBMTR consensus criteria (47) and the histopathological criteria of Slavin and Woodruff (52). Chronic graft vs. host disease will be diagnosed and graded using the staging criteria developed by Sullivan et al (53).
- 4) The responses of the EBV lymphomas will be identified as complete remission, partial remission, stable disease, or no response with disease progression based on the following criteria:

- Complete remission: Complete resolution of all clinical and radiologic evidence of lymphoma, confirmed by biopsy of affected tissues when indicated, lasting for at least three weeks following completion of a course of cell infusions.
- Partial remission: A 50% or greater reduction in the size of all lymphomatous lesions as determined by CT or MRI based measurements of tumor volume, which is maintained for at least three weeks following completion of a course of cell infusions.
- Stable disease: Less than 50% reduction of lymphomatous lesions without progression at any site maintained for at least 3 weeks following completion of a course of cell infusions.
- No response with disease progression: Progressive enlargement of one or more lymphomatous lesions by three weeks following a course of T-cell infusions.

5) For recipients of HSCTs, and other severely immunocompromised patients who have high and increasing levels of EBV DNA in the blood, without clinical or radiological evidence of tumors, who are treated preemptively with EBV-Specific T cells, a therapeutic response will be defined as:

- Viral - Complete Response: Clearance of EBV without subsequent development of EBV LPD
- Viral - Partial Response: At least a ten-fold decrease in EBV DNA levels
- Viral - Stable Response: Persistence of circulating EBV DNA without development of EBV LPD
- Viral - No Response with Progression: Persistence of EBV DNA with subsequent development of EBV LPD

## **BIOSTATISTICS**

This study is being conducted on two patient groups: (1) Marrow graft recipients and patients with severe congenital or anti-neoplastic drug induced immunodeficiency who are likely to be durably engrafted and are therefore at risk for GvHD; and (2) Organ graft recipients and AIDS patients who will almost invariably reject the infused T-cells and are therefore at very low risk of GvHD. For the patients in Group 2, this is a continuing Phase I study to determine the Maximally Tolerated Dose (MTD) of EBV-specific T-cells in the treatment of EBV induced lymphomas.

In order to find the MTD for Group 2, a dose escalation scheme is being employed with patients entering in cohorts of three, at each starting dose level (see Section IV of the Treatment Plan). Dose escalation is based on the Dose Limiting Toxicity (DLT), which is defined as a grade 3-4 toxicity at either the initial or second course of EBV-specific T-cell infusion. The dose escalation scheme for this study is as follows:

- If none of three patients experience DLT at a given dose level, then proceed to the next starting dose level.
- If one of three patients experience DLT at a given dose level, three additional patients will be treated at that dose level. If none of these three experience DLT, the dose is further escalated.

- If two or more of the six patients experience DLT at a given dose level, the MTD is defined as the previous dose level.

In the event that only three patients are treated at the MTD, an additional three patients will be treated at that level. If among these six patients, two or more experience DLT, the MTD will be lowered and the same criterion will be applied to the previous dose level.

The probability of escalating to the next higher dose level, based on the true risk of a DLT at the current level, is given in the table below. As the table shows, escalation to the next dose level is probable if the risk of DLT is low, and the likelihood of escalation decreases as the risk of DLT increases.

True Risk of Toxicity	.10	.20	.30	.40	.50	.60
Probability of Escalation	.87	.66	.42	.23	.11	.04

A minimum of 3 patients and a maximum of 18 patients will be treated in each of the two study groups. It is expected that each study will accrue 9 patients per year and will last approximately 1-2 years.

For patients in Group I, the phase II aspect of the trial will accrue a minimum of 20 patients and a maximum of 47 patients. We observed a complete remission rate using a Simon two-stage design. We will enroll 20 patients in the first stage. If 8 or more achieves CR then we will enroll 27 more for a total of 47 patients. If there are at least 20 patients achieving CR then we will recommend this regimen for further evaluation. This design has 90 % power to distinguish between CR rates of 35 % and 55 % with a Type I error of 10 %.

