2.3 Sample Size

The initial rationale for the sample size of this study was the following: For subjects in group 1, the phase 2 portion of the study was to accrue a minimum of 20 subjects and a maximum of 47 subjects, using a Simon two-stage design. Enrollment of 20 subjects is needed in the first stage. If 8 or more subjects achieve CR then we 27 additional subjects will be enrolled, for a total of 47 subjects. If at least 20 subjects achieve CR then this regimen will be recommended for further evaluation. This design has 90% power to distinguish between CR of 35% and 55% with a type I error of 10%.

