4.1 Full Analysis Sets

The Full analysis set is defined as all subjects who received at least 1 dose of study treatment. All efficacy and safety analyses will use the full analysis set except for the endpoints of DOR and TTR, which will be conducted on the subjects in the full analysis set with an objective response (CR or partial response [PR]).

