11 CHANGES FROM PROTOCOL-SPECIFIED ANALYSIS

This study was originally designed and performed at a single academic center. Other than the primary endpoint of CR, specific endpoints and analyses of efficacy and safety data were not defined in the protocol. Therefore, Atara has defined these statistical components in this SAP, including the following:

- No formal hypothesis test will be conducted on CR, although the sample size calculation is a two-stage design based on CR. Point estimates and CIs will be provided for the rates of CR/PR for the cohorts and combined cohorts defined in Section 4.2 whenever feasible. In addition, statistics for the DOR and durable response are also provided.
- In the protocol, the primary objective included assessment of CR. To be consistent with Atara's other tabelecleucel studies, ORR is considered as the primary endpoint.
- All the analyses will be presented by the cohorts and cohorts combined defined in this SAP (Section 4.2), not by the groups defined in the protocol.

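### The Group I Simon rule of at least 20 CRs in 47 has a type I error of about 14%, not the stated 10%; with the other design numbers unchanged, only at least 21 meets both stated properties

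*Protocol*

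**What the plan says.** The protocol's BIOSTATISTICS section sets out a Simon two-stage design for the Group I phase II part:

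- Stage 1: "We will enroll 20 patients in the first stage". Accrual continues if at least 8 of them reach CR.
- Stage 2: 27 more patients, 47 in total.
- Final decision: "If there are at least 20 patients achieving CR then we will recommend this regimen for further evaluation".
- Claimed properties: 90% power to tell a CR rate of 55% from one of 35%, "with a Type I error of 10" percent.

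SAP 2.3 presents the same design as the initial rationale for the sample size. It keeps the final cut-off ("If at least 20 subjects achieve CR then this regimen will be recommended for further evaluation") and the claim ("This design has 90% power to distinguish between CR of 35% and 55% with a type I error of 10" percent).

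SAP 11 then limits how the rule is used: "No formal hypothesis test will be conducted on CR, although the sample size calculation is a two-stage design based on CR". It makes ORR the primary endpoint but still promises CR/PR estimates: "Point estimates and CIs will be provided for the rates of CR/PR for the cohorts and combined cohorts defined in Section 4.2 whenever feasible".

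**The concern.** A Simon design is usually tabulated by the largest response count at which the regimen still fails at each stage. A protocol that words its rule as a minimum count for success must add one to both limits. Here the first-stage limit reads like a success count and the final limit reads like a failure count, so the stated error rates may belong to a different rule from the one written.

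What is at stake is the false-positive rate attached to a go/no-go threshold. If the final cut-off is one too low, a regimen with a true CR rate of 35% is recommended more often than the documents say. Anyone who sets the CR count against the published boundary would then rely on a wrong figure.

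**Working it through.** **Inputs** (protocol BIOSTATISTICS, repeated in SAP 2.3): first stage n1 = 20; continue if X1 ≥ 8; second stage 27, so N = 47; recommend if the total number of CRs is at least k = 20; p0 = 0.35; p1 = 0.55. All inputs are stated, so none is assumed. A single-arm rule that recommends only for high CR counts is one-sided by construction, so sidedness does not enter.

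**Formula.** With X1 ~ Bin(20, p) and X2 ~ Bin(27, p),

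P(recommend | p) = Σ over x = 8 to 20 of P(X1 = x) · P(X2 ≥ k − x).

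The type I error is this probability at p = 0.35, and the power is its value at p = 0.55.

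**Attempt to reproduce the stated 10% and 90%.** First stage and N are as written; only the final cut-off varies:

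| Final cut-off k | Type I error | Power | Meets ≤10% and ≥90%? |
|---|---|---|---|
| ≥19 | 0.1974 | 0.9347 | no |
| ≥20 (as written) | 0.1417 | 0.9246 | no |
| ≥21 | 0.0938 | 0.9049 | yes |
| ≥22 | 0.0571 | 0.8707 | no |

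The written rule does not reproduce the stated type I error; it exceeds it by 14.2 − 10 = 4.2 percentage points. The stated pair is met only at k = 21. With k = 20 the type I error would be 8.7% at a null CR rate of 33% and 11.2% at 34%, so the written rule has a 10% error for a null somewhere between those rates, not for 35%.

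**Could the slip lie elsewhere?**

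- *First-stage rule*, keeping at least 20 of 47:

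| Continue if | Type I error | Power |
|---|---|---|
| ≥7 of 20 | 0.1621 | 0.9546 |
| ≥8 of 20 | 0.1417 | 0.9246 |
| ≥9 of 20 | 0.1091 | 0.8590 |
| ≥10 of 20 | 0.0708 | 0.7460 |

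  Both columns fall as the first-stage cut-off rises. Power is already below 90% at ≥9, before the type I error reaches 10%, so no first-stage cut-off gives both.
- *No early stop* (47 patients in a single stage, at least 20 CRs): 0.1749 and 0.9684, which is further from 10%.
- *Total N*, keeping ≥8 of 20 and ≥20 overall: N = 44 gives 0.0875 and 0.8914; N = 45 gives 0.1046 and 0.9060. Neither meets both, and the documents are consistent on 20 + 27 = 47.

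**Where the numbers probably come from.** A search for the two-stage design with the smallest expected sample size at 35%, subject to type I error ≤ 10% and power ≥ 90%, returns n1 = 20, continue at ≥8, N = 47, succeed at ≥21. The probability of stopping at stage 1 under 35% is 0.601, so the expected N is 20 + (1 − 0.601) × 27 = 30.8. In failure-count notation this design is 7/20 and 20/47. Those are the trial's own numbers, with 7 converted to 8 for success and 20 left unconverted. This is an inference; the documents do not give the source of the design.

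**Where the two cut-offs differ.** They disagree only if the trial continues and ends with exactly 20 CRs in 47 (20/47 = 42.6%). The probability of that outcome is 0.1417 − 0.0938 = 0.0479 at a true rate of 35%, and 0.9246 − 0.9049 = 0.0197 at 55%.

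**The case against.** The arithmetic cannot reasonably be disputed. The case on the other side concerns consequence and remedy.

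1. *The SAP does not use the rule.* SAP 11 drops the formal CR test and makes ORR primary, SAP 4.2 analyses by cohort instead of protocol group, SAP 5 plans no formal interim analysis, and SAP 2.3 labels the passage an initial rationale. This stands, and it keeps the point well short of invalidating the analysis. It does not make the stated error rate correct. The decision rule remains in the protocol, and the SAP restates its properties as fact.
2. *Only one outcome is affected.* This is true. The 4.8-point probability of that outcome at 35% is the whole difference between 14.2% and 9.4%.
3. *Moving a boundary late is improper.* SAP 4.2 already marks which cohorts have enrolled subjects, and the SAP approvals are dated July 2019. Changing 20 to 21 now would be retrospective, and doing so in the SAP alone would create a conflict with the protocol. This is a good reason to prefer restating the properties.
4. *The corrected figures assume that the first-stage stop was applied.* This also stands. Without the stop, ≥21 of 47 has a type I error of 10.9%, slightly above 10%. The stop is part of the design as stated, but the documents do not show whether it was applied.
5. *The documents do not say which number is the slip.* Correct: either the cut-off or the stated error rate could be the one to change. The mismatch holds in both cases.

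**Conclusion.** The stated type I error is wrong for the stated rule in both documents. As written, a regimen with a true CR rate of 35% would be recommended 14.2% of the time instead of 10%; power is 92.5%, so the 90% claim is met. With the same first stage and N, at least 21 is the only final cut-off that delivers both claimed properties (9.4% and 90.5%).

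The result rests on exact binomial probabilities, independent patients with a common CR rate, and a first-stage stop applied as described. The off-by-one explanation is likely but is not needed for the conclusion. Because the formal CR test has been dropped and only a result of exactly 20 in 47 is affected, this should be fixed but does not threaten the planned analyses.

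**What to change.** Choose one of two corrections:

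- **Restate the properties (safer at this stage).** Keep at least 20 and change the stated figures in protocol BIOSTATISTICS and SAP 2.3 to a type I error of about 14% and power of about 92%. Cost: two percentages in two places, with no change to the rule.
- **Correct the cut-off.** Change 20 to 21 in both places together, so that protocol and SAP stay consistent. Cost: one number in each document; power falls from 92.5% to 90.5%. The change should be described as retrospective.

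In either case, add one sentence to SAP 11 that discloses the discrepancy and states that the figures assume the first-stage stop was applied. No extra patients or data are needed.

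Showing the Group I phase II CR count beside the boundary is optional and would be descriptive only. It would first need a defined denominator, because the SAP analyses by cohort and its only analysis set covers everyone treated ("The Full analysis set is defined as all subjects who received at least 1 dose of study treatment").

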### **RISKS:**

- 1) **Acute Toxicities:** The EBV-specific T-cells to be used for adoptive immunotherapy are activated T-cells potentially capable of generating significant quantities of cytokine such as IL-2, IFN- $\gamma$  and TNF. **These cytokines may acutely induce fever and could potentially cause hypotension and other manifestations of shock, including toxicity to the lung.** However, experience with infusions of CMV-specific T-cells (45), *in vitro* expanded tumor infiltrating T-cells (54) and existing limited studies of adoptively transferred EBV-reactive T-cells, either as purified fractions or in donor leukocytes (34,46) suggest that these infusions will be well tolerated, with a low risk of systemic toxicity. However, in critically ill patients, toxicities could be more frequent and severe.
- 2) **Organ Allograft Rejection Crises:** Patients receiving EBV-specific T-cell infusions for treatment of monoclonal EBV-lymphomas complicating the immunosuppression used to sustain an organ allograft may be at risk of an acute rejection episode following infusion of the T-cells. Such episodes could be precipitated if significant numbers of alloreactive T-cells are present in the T-cell inoculum. It is also possible that the EBV-specific T-cells, upon interaction with their targets, will generate cytokines capable of stimulating alloreactive host T-cells that have been suppressed by drugs used to prevent rejection. If a rejection crisis is precipitated, it will be treated with prednisone and/or anti-thymocyte globulin as recommended by the patient's transplant physician.
- 3) **Graft Versus Host Disease:** Acute Graft Versus Host Disease (GvHD) represents an immune assault induced by engrafted alloreactive donor T-lymphocytes, against host alloantigens predominantly expressed on hematopoietic cells and their tissue-based progeny. It is

manifested by skin rash, hepatitis, enteritis and suppression of host hematopoietic and lymphoid tissues resulting in blood count depressions or aplasia and prolonged immunodeficiency.

The development of GvHD necessitates engraftment and proliferation of donor alloreactive T-cells. Patients who have received organ allografts and even the most severely immunodeficient AIDS patients are able to reject allogeneic lymphoid cells. Despite a large documented experience of transfusions of unirradiated cells, no instance of GvHD has been recorded in AIDS patients or recipients of kidney, lung, heart, or liver grafts (39). Thus, these patients are likely not at risk for this complication.

Marrow transplant recipients and children with severe combined immunodeficiency, on the other hand, are at risk of acute and chronic forms of GvHD if infused with unirradiated HLA-matched or HLA-mismatched T-cells capable of responding to host alloantigens. Acute GvHD affects 60% of recipients of HLA-matched marrow grafts. Up to 85% of adults transplanted with HLA-matched marrow from unrelated donors or partially matched related donors will develop moderate to severe (grade II-IV) acute GvHD despite drug prophylaxis (55). This complication is a principal contributor to mortality in 40-50% of cases. Furthermore, 50% of the survivors of acute GvHD will develop manifestations of chronic GvHD (56).

The *in vitro* propagation of T-cells reactive against autologous EBV-transformed cells selects for the expansion of EBV-specific T-cells and the elimination of other T-cells, including alloantigen-responsive T-cells (46). As a result, infusions of virus-specific T-cells generated over 4-6 weeks *in vitro* have thus far not been complicated by GvHD in marrow transplant patients. Nevertheless, there is a risk that small numbers of alloreactive T-cells could be transferred with the infusions of EBV-specific T-cells. To counter this risk, only HLA compatible or HLA haplotype matched donors will be used as donors of EBV-specific T-cells and only EBV-specific T-cells tested to be free of cells reactive against allogeneic cells will be administered to patients who could be durably engrafted following a T-cell infusion.

- 4) **Transmission of Infection:** There is a potential that transfusions of white cells or T-lymphocytes may also serve as vectors of serious infection. All precautions to maintain sterility will be taken.
- 5) **Transfusion Reactions:** It is possible that during the course of repeated infusions of EBV-specific T-cells derived from a normal donor, the host will develop an immune response against the donor cells, which could lead to an immediate allergic response, manifested by generalized urticaria of the skin, angioneurotic edema, or more serious manifestations such as bronchospasm or hypotension. Such reactions will be treated symptomatically.
- 6) **Treatment Failure:** Treatment with EBV-specific T-cells may not alter the progression of EBV lymphoma or may induce only transient regressions of disease. Furthermore, because of host immune responses to donor cells, secondary or subsequent treatment by this adoptive immunotherapeutic approach may be precluded.

## **RESEARCH PARTICIPANT REGISTRATION**

Confirm eligibility as defined in the section entitled Criteria for Patient/Subject Eligibility.

Obtain informed consent, by following procedures defined in section entitled Informed Consent Procedures.

During the registration process registering individuals will be required to complete a protocol specific Eligibility Checklist.

All participants must be registered through the Protocol Participant Registration (PPR) Office at Memorial Sloan-Kettering Cancer Center. PPR is available Monday through Friday from 8:30am – 5:30pm at PPD [REDACTED]. Registrations must be submitted via the PPR Electronic Registration System PPD [REDACTED]. The completed signature page of the written consent/RA or verbal script/RA, a completed Eligibility Checklist and other relevant documents must be uploaded via the PPR Electronic Registration System.

### **RANDOMIZATION**

N/A

### **DATA MANAGEMENT ISSUES**

This is a single institution trial and all patients will be treated at Memorial Sloan-Kettering Cancer Center.

A research Study Assistant (RSA) will be assigned to this study. The responsibilities of the RSA include project compliance, data collection, abstraction and entry, data reporting, regulatory monitoring, problem resolution and prioritization, and coordinate the activities of the protocol study team. The data manager will also monitor laboratory compliance throughout the study. Laboratory data will be tabulated and summarized based on MSKCC normal ranges.

The data collected for this study will be entered into the MSKCC Clinical Research Data Base (CRDB).

### **QUALITY ASSURANCE**

Registration reports will be generated by the RSA on a regular basis to monitor patient accruals and completeness of the registration data. Routine data quality reports will be generated to assess missing data and inconsistencies. Accrual rates and extent and accuracy of evaluations and follow-up will be monitored periodically throughout the study period and potential problems will be brought to the attention of the study team for discussion and action.

Random-sample data quality and protocol compliance audits will be conducted by the study team, at a minimum of two times per year, more frequently if indicated.

### **DATA AND SAFETY MONITORING**

The Data and Safety Monitoring (DSM) Plans at Memorial Sloan-Kettering Cancer Center were approved by the National Cancer Institute in September 2001. The plans address the new policies

set forth by the NCI in the document entitled “Policy of the National Cancer Institute for Data and Safety Monitoring of Clinical Trials” which can be found at:

<http://cancertrials.nci.nih.gov/researchers/dsm/index.html>. The DSM Plans at MSKCC were established and are monitored by the Office of Clinical Research. The MSKCC Data and Safety Monitoring Plans can be found on the MSKCC Intranet at [PPD](#)

There are several different mechanisms by which clinical trials are monitored for data, safety and quality. There are institutional processes in place for quality assurance (e.g., protocol monitoring, compliance and data verification audits, therapeutic response, and staff education on clinical research QA) and departmental procedures for quality control, plus there are two institutional committees that are responsible for monitoring the activities of our clinical trials programs. The committees: Data and Safety Monitoring Committee (DSMC) for Phase I and II clinical trials, and the Data and Safety Monitoring Board (DSMB) for Phase III clinical trials, report to the Center’s Research Council and Institutional Review Board.

During the protocol development and review process, each protocol will be assessed for its level of risk and degree of monitoring required. Every type of protocol (e.g., NIH sponsored, in-house sponsored, industrial sponsored, NCI cooperative group, etc.) will be addressed and the monitoring procedures will be established at the time of protocol activation.

